4. STATISTICAL METHODS, STUDY ENDPOINTS, AND DETERMINATION OF SAMPLE SIZE

4.1 STATISTICAL AND ANALYTICAL PLAN

Statistical analyses defined in the SAP will be performed using STATA Version 13 or newer, Rv3.2.4 or newer, and SAS version 9.4 or newer.

4.1.1 General Methods

Distribution of study parameters and covariates will be summarised depending on the type of variable with the number of subjects and the number of missing data (where relevant).

Verification of the normality of the distribution for continuous data will be carried out by graphical inspection and consideration of skewness and kurtosis measures.

Percentages will be based on the total number of non-missing values. The number missing will be presented, but without a percentage.

Descriptive statistics will be presented as;

- Discrete data: number and percentage of participants in each category
- Ordinal categorical data: number and percentage of participants in each category, median, interquartiles, range
- Continuous data: number, mean, median, standard deviation, minimum, maximum

All confidence intervals reported will be two-sided and at the 95% confidence level. There is no adjustment for multiplicity.

If not otherwise specified, the baseline value is defined as the last nonmissing value measured before administration of study drug on Day 1.

4.1.1.1 Analysis Populations

Screening population: All participants who signed the consent form and had a Screening Visit.

Intent-to-Treat (ITT): All participants who were randomised to a treatment group at the randomisation visit (visit 4).

Safety Population: All randomised participants who received at least one dose of study drug.

Evaluable Population: All participants included in the Safety Population presenting no major protocol deviations with the potential to bias the criteria for evaluation and with full follow-up.

In the event a subject receives multiple randomization assignments, the subject will be analyzed in the ITT Population according to the first assignment they received; the subject will be analysed according to what they actually received in the Safety Population; the subject will not be included in the Evaluable Population as this is a major protocol deviation.

4.1.1.2 Study Medication

For the double-blind Treatment Period, participants will be supplied with identically appearing capsules containing 290 ug linaclotide, or matching placebo.

4.1.1.3 Statistical Methods

For descriptive summaries, N will represent the total number of patients within the summarized population and n will represent the number of non-missing patients for the summarized endpoint. All summary statistics will be presented by treatment and based on non-missing endpoint values, unless otherwise specified.

Table 2. Statistical Methods

Method	Definition
Categorical Summaries	
Number and percent of patients in each category
Percent based on number of non-missing valuesNumber of missing patients in each category; percent not presented.
Continuous Summaries	
Number of non-missing patients, mean, median, standard deviation, minimum, maximum

4.1.1.4 Missing Data

Table 3. Missing data handling conventions

Endpoint Type	Descriptions
24 hour recorded girth data	Linear interpolation

4.1.1.5 Study Periods

Table 4. Study Periods

Period	Start Date	End Date
Screening	Date of Signed ICF	PreTreatment Visit Date - 7
Pretreatment	PreTreatment Visit Date	Randomization Date (up to time of randomization)
Treatment	Date of Randomization	End of Treatment Visit Date
Follow-up Period	End of Treatment Visit Date	Follow-up Phone Call

4.1.2 Demographics

4.1.2.1 Disposition of Subjects

Table 5. Disposition Analyses

Analysis Population	Description	Summary Method
Screening, ITT, Safety, Evaluable	Overall	Counts
Screening	Reason for Screening and Pretreatment Failure	Categorical Summary
ITT, Safety	Premature Discontinuation 
Completed StudyDiscontinued StudyReason for Discontinuation	Categorical Summary
ITT	Discontinuation by Time (Week) Time to D/C = 1 + <date of d/c> - <date of first dose>	Categorical Summary

The number of screen failures (i.e., participants who entered the Screening Period but not the Pretreatment Period) and the number of pretreatment failures (i.e., participants who entered the Pretreatment Period but were not randomised) will be tabulated by reason for failure.

The overall number of participants screened and the number of participants randomised to each treatment group will be presented. The number and percentage of participants included in each of the analysis populations (ITT, Safety, and Evaluable) will be presented by treatment group and overall. The number and percentage of participants who completed the study or discontinued early, including the reason for discontinuation, will be presented by treatment group and overall.

4.1.2.2 Protocol Deviations

Protocol deviations and Important Protocol Deviations (IPD) will be identified and documented for all randomized patients prior to unblinding through programmatic checks of the study data and select individual data reviews. IPDs will be determined based on review of all protocol deviations and protocol deviation categories (i.e., Use of Disallowed Medication) performed by members of the Ironwood Clinical Trials team, including but not limited to the Clinical Medical Researcher and study Biostatistician.

Table 6. Important Protocol Deviations

Analysis Population	Description	Summary Method
ITT	
Important Protocol Deviations
 
• those who entered the study even though they did not satisfy the entry criteria;• those who developed withdrawal criteria during the study but were not withdrawn;• those who received the wrong treatment or incorrect dose;• those who received an excluded concomitant treatment.• Other	Listing

4.1.2.3 Demographics and Baseline Characteristics

Participant demographics (age, sex, race, ethnicity, weight, height, and BMI [defined as weight in kg divided by height in meters squared]) and other relevant baseline characteristics will be summarized by treatment group for the ITT population.

Table 7. Demographics

Endpoint	Description	Summary Method
Age	Age at informed consent date	Continuous Summary
Sex	Male Female	Categorical Summary
Race	Caucasian Non-Caucasian Black or African American Asian American Indian or Alaska Native Native Hawaiian or Pacific Islander Other	
Ethnicity	Hispanic or Latino Not Hispanic or Latino	

Table 8. Baseline Characteristics

Endpoint	Description	Summary Method
Weight	Weight (kg)	Continuous Summary
Height	Height (m)	
BMI	BMI (kg/m ²)	
Baseline Efficacy Endpoints	Abdominal girth (measured by AUC) CSBMs (standardized weekly rate) SBMs (standardized weekly rate) Abdominal pain Abdominal discomfort Abdominal bloating Abdominal distension BSFS Note: include any measure that will be used as a baseline covariate in endpoint analyses	

4.1.2.4 Medical History

Medical History, abnormalities and surgeries, reported prior to screening occurring prior to screening will be coded using MedDRA version 19.1 or newer. Summaries will be presented by

MedDRA system organ class (SOC) and preferred term by treatment arm and overall for the safety population. Patients will be counted once per SOC and PT.

Table 9. Medical History

Parameter	Description	Summary Method
Medical History	Surgeries and Abnormalities reported at Screening SOC PT	Categorical Summaries

4.1.2.5 Prior and Concomitant Medication

Reported medication will be coded using the World Health Organization (WHO) Drug Dictionary Enhanced B2, version dated December 2016 or newer to their Anatomical Therapeutical Chemical (ATC) class and PT. Summaries will be presented by ATC and PT for the Safety Population. Patients will be counted once per ATC and PT.

Table 10. Prior and Concomitant Medication

Parameter	Description	Summary
Prior Medications	Medication taken prior to first dose of study medication	Categorical Summary
Concomitant Medication	Medication taken on or after first dose of study medication.	

4.1.2.6 Drug compliance

Patient drug compliance over the double-blind treatment period will be calculated for each patient. Dosing compliance for the Treatment Period is defined as the number of capsules actually taken by a patient during the Treatment Period divided by the number of capsules that were expected to be taken during the Treatment Period, multiplied by 100. The total number of capsules actually taken will be calculated as the total number of capsules dispensed minus the total number of capsules returned. The total number of capsules expected to be taken during the Treatment Period is the number of days between the date of first dose taken and the date of last dose taken, inclusive (i.e., last dose date – first dose date + 1). Summaries will be presented by treatment arm and overall for the Safety Population.

Table 11. Study Drug Compliance

Parameter	Description	Summary Method
Overall Drug Compliance	Percent of drug actually taken relative to amount expected to be taken in defined interval	Continuous Summary

4.1.2.7 Diary Compliance

Diary compliance will be calculated for each patient. Summaries will be presented by treatment arm over the baseline and double-blind treatment periods, and weekly, for the ITT Population. A complete Diary is defined as having responses to each of the daily Diary questions asked during the daily report.

Table 12. Diary Compliance

Parameter	Description	Summary Method
Diary Compliance Baseline (Pretreatment Period) DB Treatment Period (Weeks 1-4) Week 1 Week 2 Week 3 Week 4	Percent of completed Diary days relative to number of days in reporting interval	Continuous Summary

4.1.3 Efficacy

4.1.3.1 Analysis of Primary Efficacy Endpoint

Baseline abdominal girth (as measured by AIP AUC) will be calculated using the first 24 hours of measurements from the belt following the Baseline Visit. If an AIP increase of >4 cm is not observed over the first 24-hour period, then baseline will be defined as the 24 hours leading up to the Randomization Visit on day 1. For subjects with an AIP increase of >4 cm in both 24 hour periods, the first 24-hour period will be used.

Table 13. Primary Efficacy Analysis

Endpoint	Description	Timing	Summary Method
Change from baseline in abdominal girth at Week 4	
The mean change from randomization (Visit 4) to the end of the study (Visit 8) in abdominal girth (as measured by AUC) determined by 24-hour AIP (with hourly averages), between the linaclotide and placebo groups.
 
The AUC will be calculated using the Trapezoidal method from the first reliable hour of measurement to last measurement (bedtime). The AUC for each patient will be then individually standardised by dividing the total AUC over the period by that patient's number of hours of measurement included in the AUC.
 
In case of missing data in the middle of the valid period of measurement, AUC is calculated with linear interpolation.
	Day -1 to Day 27	Continuous summary, 95% CI

4.1.3.2 Secondary and Additional Efficacy Analyses

Baseline score for abdominal symptoms will be calculated as the average of daily values reported over the Pretreatment Period.

A patient's daily Abdominal Score is calculated as the average of the daily abdominal pain, abdominal bloating, and abdominal discomfort assessments. If two or more of these individual daily abdominal symptoms are missing, then the Abdominal Score for that day will be missing.

A patient's daily Abdominal Score plus Distension is calculated as the average of the daily abdominal pain, abdominal bloating, abdominal discomfort, and abdominal distension assessments. If three or more of these individual daily abdominal symptoms are missing, then the Abdominal Score plus Distension for the day will be missing.

Table 14. Secondary and Additional Efficacy Endpoints

Endpoint	Description	Timing	Summary Method
Change from baseline in abdominal girth at Week 2	
The mean change from baseline to the midpoint of treatment in abdominal girth (as measured by AUC) determined by 24-hour AIP (with hourly averages), between the linaclotide and placebo groups.
 
The AUC will be calculated using the Trapezoidal method from the first reliable hour of measurement to last measurement (bedtime). The AUC for each patient will be then individually standardised by dividing the total AUC over the period by that patient's number of hours of measurement included in the AUC.
	Day -1 to Day 15	Continuous summary, 95% CI
Change from Baseline in Maximal Abdominal Girth at Week 4	The maximum change in girth from the first hour, over the period from the 2 nd hour to bedtime. The percentage change in maximum distension from baseline to 4 weeks will also be calculated.	1 st hour, 2 hour to bedtime	Continuous summary, 95% CI

Table 14. Secondary and Additional Efficacy Endpoints

Endpoint	Description	Timing	Summary Method
Symptom Severity (weekly averages and change from baseline)	Each item assessed daily on 11-point NRS	Baseline, Week 1, Week 2, Week 3, Week 4; change from baseline at each postbaseline timepoint	Continuous summary, 95% CI
Abdominal pain			
Abdominal discomfort			
Abdominal bloating			
Abdominal distension			
Multicomponent scores:			
Abdominal Score			
Abdominal Score + Distension	Week 1=mean (day 1 to day 7) Week 2= mean (day 8 to day 14) Week 3= mean (day 15 to day 21) Week 4= mean (day 22 to day 28)		
	Abdominal Score: calculated weekly; the daily average of the following individual items (pain, discomfort, bloating) will be calculated, then the weekly average will be calculated as the mean of day 1 to day 7.		
	Abdominal Score plus Distension: calculated weekly; the daily average of the following individual items (pain, discomfort, bloating, distension) will be calculated, then the weekly average will be calculated as the mean of day 1 to day 7.		
	Change from baseline each postbaseline timepoint		
Change from Baseline in Digestive sensations	Change from baseline in digestive sensations (abdominal pain, discomfort, bloating and distension) at end of treatment (as measured by AUC of hourly digestive sensations)	Baseline, Week 2 (Visit 6), Week 4 (Visit 8)	Continuous summary, 95% CI
Weekly averages change from baseline in Bristol Stool Form Scale (BSFS)	Baseline= mean (day -7 to day -1) Week 1= mean (day 1 to day 7) Week 2=mean (day 8 to day 14) Week 3=mean (day 15 to day 2) Week 4=mean (day 22 to day 28) Change from baseline	Baseline, Week 1, Week 2, Week 3, Week 4, Change from baseline at each postbaseline timepoint	Continuous summary, 95% CI

4.2 SAMPLE SIZE JUSTIFICATION

A total of 40 (20 in each group) participants are required to complete the study, with 120 needed to enter screening to account for ineligible participants and dropouts.

To achieve 80% power to detect a difference of 2.2 cm or more (using a simple 2-sided t-test with estimated SD = 2.4 cm and the conventional 5% significance level) in the mean change in abdominal girth (as measured by AIP AUC) from the start to the end of the day, between the active and placebo groups, 20 participants per group (40 participants in all) are required. Assuming a 15% dropout rate, 47 participants would need to be randomised to yield 40 evaluable participants. Estimating a 60% screen/pretreatment failure rate (mostly from failure to meet distension criteria, but also pretreatment abdominal pain, abdominal bloating, and bowel movement criteria), 120 participants would need to enter screening to achieve 40 randomised participants.

Note: for a previous yogurt study, a mean difference in girth of 1.6 cm (SD = 2.4 cm) was observed

Sample size calculated using nQuery Advisor 3.0.

Note: Due to difficulties with enrollment, the study was terminated by the sponsor after 20 subjects were randomized.

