At the Screening Visit, all ongoing medicines taken by the participant will be recorded. Any over-the-counter or prescription laxatives, suppositories, or enemas used to treat IBS-C may not be used on the calendar day before the Pretreatment Visit. Other prohibited medicines may not be used during the 14 calendar days before the Pretreatment Visit.

A complete list of drugs that are conditionally allowed as concomitant medicines for either episodic or chronic use or as Rescue Medicine is provided in Appendix 1. Prohibited concomitant medicines are also included in Appendix 1.

During the Pretreatment and Treatment Periods, participants may use dispensed, protocoldefined laxatives (bisacodyl tablets or suppositories) as Rescue Medicine when at least 72 hours have passed since their previous BM or when their symptoms become intolerable. In order to qualify for randomisation into the Treatment Period, participants must not have used Rescue Medicine on the calendar day before the Randomisation Visit and on the day of the Randomisation Visit up until the time of the clinic visit. Participants must agree to refrain from using Rescue Medicine from the time of the clinic visit through the calendar day after randomisation. Furthermore, participants will be asked to refrain from using Rescue Medicine on the day before, day of, and day after each AIP measurement.

Any changes in concomitant medicines or new medicines added from the Screening Period through the Follow-up Period will be recorded on the CRF. Concomitant medicines will be recorded at all study visits throughout the entire study. Rescue Medicine will be documented by the participant on the Rescue Medicine record form.

Planned Number of Participants:

In order to ensure that 40 participants have completed the study as planned, up to 120 participants may need to be screened.

Diagnosis and Main Criteria for Inclusion:

Inclusion Criteria:

To be eligible to participate in the study, participants must meet all of the following criteria:

- 1. Participant has provided written informed consent before participating in the study after being given a full description of the study and prior to any study-specific procedures being performed.
- 2. Participant is a male or non-pregnant, non-breastfeeding female, and is age 18 years or older (no upper age limit).

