5. STUDY DESIGN

5.1 OVERALL STUDY DESIGN AND PLAN: DESCRIPTION

The study will be a single-centre, randomised, double-blind, placebo-controlled, parallel-group study comparing linaclotide to placebo. Approximately 40 participants with a diagnosis of IBS-C (Rome III criteria), who are shown to distend >4 cm over 24 hours during the Pretreatment Period, will be randomised.

The study will consist of up to 14 days of screening, 7 days of pretreatment, 29 (\pm 2) days of double-blind treatment, and 7 (\pm 2) days of follow-up. At the end of the Pretreatment Period, participants meeting the entry criteria for this study will be randomised (1:1) to one of two double-blind treatment groups: 290 ug linaclotide or matching placebo.

Figure 2. Study Schedule and Chronology

Note: There is no Day 0

** AIP Belt Measurement

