11.1 DETERMINATION OF SAMPLE SIZE

A power calculation was used to determine how many participants will be required, as can be seen below. A total of 40 (20 in each group) participants are required to complete the study, with 120 needed to enter screening to account for ineligible participants and dropouts.

To achieve 80% power to detect a difference of 2.2 cm or more (using a simple 2-sided t-test with estimated SD = 2.4 cm and the conventional 5% significance level) in the mean change in abdominal girth (as measured by AIP AUC) from the start to the end of the day, between the active and placebo groups, 20 participants per group (40 participants in all) are required. Assuming a 15% dropout rate, 47 participants would need to be randomised to yield 40 evaluable participants. Estimating a 60% screen/pretreatment failure rate (mostly from failure to meet abdominal girth criteria, but also pretreatment abdominal pain and abdominal bloating criteria), 120 participants may need to enter screening to achieve 40 randomised participants.

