5. CHANGES FROM ANALYSES PLANNED IN THE PROTOCOL

The following analyses differ compared to those specified in the study protocol:

- All continuous data, regardless of normality, will be presented as number, mean, standard deviation, and range. Protocol had stated continuous, non-normally distributed data would be presented as number, median, interquartiles, and range.
- [Section 11.3.4 of the Protocol](#) states that change from baseline will be calculated for clinical laboratory evaluations. Clinical labs were only taken at screening and therefore, no change values will be calculated.
- The following secondary efficacy endpoints have been renamed:
 - ‘Change from baseline in abdominal distension at week 2’ will now be referred to as ‘change from baseline in abdominal girth at week 2’
 - ‘Change from baseline in maximal abdominal distension at week 4’ will now be referred to as ‘change from baseline in maximal abdominal girth at week 4’
 - ‘Change from Baseline in digestive sensations at weeks 4 and 8’ was an error as the study is only 4 weeks in duration. This should have been ‘Change from baseline in digestive sensations at week 2 (Visit 6) and week 4 (Visit 8)’.
 - ‘Change from baseline in Bristol Stool Form Scale at weeks 4 and 8’ was an error as the study is only 4 weeks in duration. This should have been ‘Change from baseline in Bristol stool form scale at week 2 (Visit 6) and week 4 (Visit 8)’.
 - Change from baseline in Bristol Stool Form Scale at Weekk 2 and 4 will be analyzed using linear mixed models with appropriate contrasts. The Protocol had previously specified generalized estimating equations (GEE) would be used for analysis.
- The HADS and IBS-SSS were assessed at Screening and EOT. These values will not be analyzed.

- **Section 11.3.3.5 of the Protocol** reports additional analysis that will be conducted. Specifically, it states, “The relationship between the hourly digestive sensation scores for bloating and the corresponding hourly difference in girth measures from hour 1 over the relevant time period during each of the two 24-hour periods at visit 4 and visit 8 will be assessed using longitudinal regression analysis.” This analysis will no longer be conducted.
- Given that the study was terminated by the sponsor after only 20 patients were randomized, there will be no formal statistical modeling (ANCOVA, MMRM) and descriptive statistics and confidence intervals will be presented only.

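### The plan gives both 47 and 40 as the number to randomise; with 40 randomised and its own 15% dropout, power is about 74%, not 80%.

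*SAP*

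**What the plan says.** The sample size paragraph in SAP 4.2 starts from "To achieve 80% power to detect a difference of 2.2 cm or more", with SD 2.4 cm and a two-sided 5% t-test, and arrives at 20 per group. The 40 are participants who complete the study. Two statements about the number to randomise then stand next to each other:

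- "Assuming a 15% dropout rate, 47 participants would need to be randomised to yield 40 evaluable participants".
- After a 60% screening and pretreatment failure rate, "120 participants would need to enter screening to achieve 40 randomised participants".

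The Protocol synopsis (Sample Size Determination) and Protocol 11.1 have the same pair; in 11.1 the second statement reads "120 participants may need to enter screening to achieve 40 randomised participants". The design descriptions in Protocol 5.1 and SAP 3.1 give only the lower figure as the number to be randomised: "Approximately 40 participants with a diagnosis of IBS-C (Rome III criteria), who are shown to distend >4 cm over 24 hours". The synopsis entry on planned numbers again treats 40 as completers: "In order to ensure that 40 participants have completed the study as planned, up to 120 participants may need to be screened".

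SAP 4.2 also records that "the study was terminated by the sponsor after 20 subjects were randomized". SAP section 5 lists changes from the Protocol and corrects some of its wording errors, but does not mention the 47 and the 40.

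**The concern.** The number to randomise and the number to analyse are different quantities, and the gap between them is the dropout allowance. The documents use 40 for both. A reader who takes about 40 randomised as the target, which is the only figure in the design sections, would credit the design with 80% power when its own 15% dropout leaves fewer than the 40 evaluable participants that figure needs.

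The planned size is also the yardstick for the early stop. Twenty randomised is 20/47 = 43% of one target and 20/40 = 50% of the other. A study report that draws on SAP 3.1 and 4.2 would carry both.

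**Working it through.** **Inputs, all from SAP 4.2 and repeated in Protocol 11.1:** difference 2.2 cm; SD 2.4 cm; two-sided 5% two-sample t-test; 20 evaluable per group; 15% dropout; 60% screening and pretreatment failure; 120 screened. Allocation is 1:1 (Protocol 5.1, SAP 3.1).

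**1. Reproduce the plan's figure.** Power comes from the noncentral t distribution with n1 + n2 − 2 degrees of freedom and noncentrality 2.2 / (2.4 × √(1/n1 + 1/n2)).

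- 20 and 20: noncentrality 2.90, 38 degrees of freedom, power 80.6%.
- 19 and 19: power 78.5%.

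Twenty per arm is therefore the smallest equal group size that reaches 80%. The stated 40 evaluable reproduces, with almost no slack.

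**2. Dropout.**

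- 40 / 0.85 = 47.06, which the plan gives as 47.
- 47 × 0.85 = 39.95, about 40 evaluable.
- 40 × 0.85 = 34, or 17 per arm, which is six short of the 40 required.

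**3. Screening.**

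- 120 × (1 − 0.60) = 48 randomised, and 48 × 0.85 = 40.8 evaluable.
- 47 / 0.40 = 117.5 screened for 47 randomised, close to the stated 120.
- 40 / 0.40 = 100 screened for 40 randomised, not 120.
- 40 randomised out of 120 implies a failure rate of 1 − 40/120 = 66.7%, against the stated 60%.

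**4. The two readings compared.**

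| Randomised | Screened at 60% failure | Evaluable at 15% dropout | Power for 2.2 cm |
|---|---|---|---|
| 47 | 117.5 | 39.95 (about 20 per arm) | 80.6% at 20 per arm |
| 40 | 100 | 34 (17 per arm) | 73.6% |

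The noncentrality for 17 per arm is 2.67 on 32 degrees of freedom. A normal approximation gives 76.2%, also below 80%.

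The dropout rate, the number screened and the completer requirement all fit 47 or 48 randomised. None of them fits 40.

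**The case against.** The strongest reply is that no sentence attaches 80% power to 40 randomised. The plan ties the 80% to 20 per group, calls those participants evaluable, and inflates them to 47 in the next sentence, so the power calculation itself is sound. The screening arithmetic was evidently built on 47 or 48, and the 40 in that sentence is probably a slip for 40 evaluable or 47 randomised. This much stands: the defect lies in the stated number to randomise, and the 74% applies only if 40 is taken as the target. It does not dispose of the point, because Protocol 5.1 and SAP 3.1 separately give about 40 as the number randomised, and 47 is 17.5% above 40, too far for the word approximately to cover.

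The 74% also assumes that dropouts leave the analysis. The Protocol allowed multiple imputation and analysis of the ITT Population (11.3.3), and a covariate-adjusted primary analysis (11.3.3.2). That is a fair qualification, but the unadjusted t-test on evaluable participants is the plan's own sizing basis.

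Two smaller points are correct. Rounding 47.06 up gives 48, and 39 evaluable split 20 and 19 would have 79.6% power, so 47 meets the target only to rounding. And nothing practical now depends on the number, since under SAP section 5 "there will be no formal statistical modeling (ANCOVA, MMRM) and descriptive statistics and confidence intervals will be presented only".

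**Conclusion.** The concern holds, as a minor point. Five places (the Protocol synopsis, Protocol 5.1 and 11.1, SAP 3.1 and 4.2) give 40 or about 40 as the number randomised. That conflicts with the 47 stated in three of them and with the plan's own dropout, screening and completer figures.

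Taken literally, 40 randomised means 34 evaluable and 73.6% power, about 7 percentage points below the 80.6% available with 20 per arm. This rests on a 2.2 cm difference, SD 2.4 cm, a two-sided 5% t-test, a 15% loss shared equally between arms, and no contribution from dropouts.

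The effect is on the record only. With enrolment ended at 20 and formal modelling dropped, no recruitment decision, estimate or interval changes.

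**What to change.** Use one chain throughout: 120 screened, about 47 randomised, 40 evaluable.

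- In the Protocol synopsis, Protocol 11.1 and SAP 4.2, change the screening sentence so that 120 screened leads to 47 randomised.
- In Protocol 5.1 and SAP 3.1, change about 40 to about 47 and mark it as the planned number.
- In SAP 4.2, label the 80% as the original design figure, so that it is not read as applying to the 20 randomised.

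If the sponsor prefers not to reissue the Protocol after enrolment has ended, a correcting sentence in SAP section 5 would put the right chain on record.

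If 40 randomised really was intended, the text should give its consequences: 100 screened, 34 evaluable and about 74% power. That is a weaker design and would also require withdrawing the statements that 40 must complete, so it is the less natural repair.

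Optionally, SAP 4.2 could add that with 20 randomised, and SD 2.4 cm assumed, power for 2.2 cm is about 49% with none lost (10 per arm) and about 42% with 15% lost (9 and 8).

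The cost is text only: no extra participants and no change to any analysis.
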